[name] [name]	AON will advise on data collection for WP2 and contribute to meetings and outputs for WP1 and WP2.	Ad-Hoc	
Experts-by-experience: two experts-by-experience will be invited to be members of the research team.			
[name]	Research Associate	variable	
[name]	Research Assistant	1	
[name]	Research Assistant	1	
[name]	PhD Student (formative process evaluation)	1	

KEY WORDS

Social care; prison; feasibility study; realist; randomised control trial.

STUDY FLOW CHART

Empowered Together (ET) Intervention

ET follows the TIP principles: 1. Trauma informed; 2. Integrated; 3. Person-centred.

WP1: Preliminary Work - Months 1-6

- 1.1. Development of supervision and training manual for ET workers
- 1.2. Development of fidelity scale
- 1.3. Development of immersive film, event, blog and website

Capacity building
PPIE meetings and evaluation
Immersive film, event, blog and website development
Steering group meetings

WP2: Feasibility RCT and Embedded Process Evaluation - Months 7-16

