2.2 Outcome Measures

Primary Outcomes

WP1:

- A training and supervision manual (nine months after project commencement)
- A fidelity of implementation tool; this will be completed by a researcher in WP2 at the end
 of the three-month intervention to assess whether the intervention has been delivered in
 accordance with the protocol and manual, and to evaluate the quality of delivery
- Audio, blog, event, film, webpage content (18 months after project commencement)

WP2:

For the feasibility RCT, the below traffic light criteria will be used in the decision-making process. However, outcomes will be reviewed as a whole, such that amber or red ratings on one or more of the objectives will not necessarily prevent progression to a full trial:

- Delivery of ET at each site (at end of feasibility RCT)
 - o Green: both sites able to deliver ET
 - o Amber: one site able to deliver ET
 - o Red: no sites able to deliver ET
- Number screened, eligible, and recruited into trial (once marked eligible from screening)
 - o Green: 60% of participants recruited
 - Amber: 40-60% of participants recruited
 - o Red: <40% of participants recruited
- Outcome measure completion rates (at 42- and 90-days ±7 days post-randomisation)
 - o Green: 80% of participants have completeness of >60%
 - o Amber: 60-80% of participants have completeness of >60%
 - o Red: <60% of participants have completeness of >60%
- Intervention adherence and fidelity (at end of feasibility RCT)
 - o Green, amber, and red ratings will be based on the bespoke fidelity tool; as such, the progression criteria will be developed once the tool has been finalised.
- Retention rates (at 90-days ±7 days post-randomisation)
 - o Green: 60% of participants
 - o Amber: 40-60% of participants

- o Red: <40% of participants
- Proportion transferred and/or released during follow-up (at 42- and 90-days ±7 days postrandomisation)

Outcome measures for the cost-effectiveness feasibility analysis will include:

- Completeness of care plans, case notes, and resource use questionnaires
- Potential cost of ET (based on data from the Personal Social Services Resource Unit)
- Assessment of the feasibility of conducting a Budget Impact Analysis (BIA)
- List of suitable variables for a social Return On Investment (ROI) analysis

Outcome measures for the realist-informed process evaluation will include:

• Refined IPT, logic model, and intervention delivery platform.

Secondary Outcomes

WP2:

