2.3 Table of Endpoints and Outcomes

Objectives	Outcome Measures	Timepoints of Evaluation
WP1: Primary Objective: to develop	Training and supervision manual for ET workers	9 months after project commencement
communication, training, and trial	Fidelity of implementation tool	9 months after project commencement
materials	Audio, blog, event, film, and webpage content	18 months after project commencement
WP2: Primary Objective: to determine	Delivery of ET at each site	At end of nine-month feasibility trial period
the acceptability and feasibility of a full RCT	Number screened, eligible, and recruited	At end of feasibility trial period
	Outcome measure completion rates	Baseline, 42-days (±7 days), and 90- days (±7 days) post-baseline
	Intervention adherence and fidelity (based on bespoke fidelity tool)	At end of nine-month feasibility trial period
	Retention rates	90-days (±7 days) post-randomisation
	Proportion transferred or released during follow-up	At end of nine-month feasibility trial period
	Completeness of care plans, case notes, and	18 months after project commencement

	resource use questionnaires	
	Potential cost of ET BIA feasibility	18 months after project
		commencement 18 months after project
	assessment	commencement
	List of suitable variables	18 months after project
	for a social ROI	commencement
	Refined IPT, logic model,	18 months after project
	and delivery platform	commencement
WP2: Secondary Objective: to collect patient outcomes data to inform a full RCT, including assessing the acceptability of the measures used	CANFOR-R	Baseline, 42-days (±7 days), and 90-
		days (±7 days) post-baseline
	ASCOT SCT4	Baseline, 42-days (±7 days), and 90-
		days (±7 days) post-baseline
	EQ-5D-5L	Baseline, 42-days (±7 days), and 90-
		days (±7 days) post-baseline
	ICECAP-A	Baseline, 42-days (±7 days), and 90-
		days (±7 days) post-baseline
	ReQoL-10	Baseline, 42-days (±7 days), and 90-
		days (±7 days) post-baseline
	Resource usage	Baseline, 42-days (±7 days), and 90-
		days (±7 days) post-baseline

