9. STATISTICS AND DATA ANALYSIS

9.1 Sample Size Calculation

WP1:

The estimated sample size for the workshops for developing the manual for ET workers is N=12, whilst that for the workshops for developing the audio, blog, and film content is N=8. These group sizes will allow for effective communication, diverse perspectives, and meaningful participation.

WP2:

For the feasibility RCT, the target sample size target is N=76 (N=38 per arm). This has been derived from use of a traffic light system to determine whether an RCT is feasible. It is based on the feasibility objectives in relation to the RAG criteria that tests against being in the RED zone (unacceptable outcome) based on an expectation of being in the GREEN zone (acceptable outcome), along with the sample size to give high power to reject being in the RED zone if the GREEN zone holds true (3). The three key feasibility objectives are to assess: (i) recruitment uptake (percent of screened patients recruited), (ii) treatment fidelity, and (iii) participant retention (follow up):

i. Based on the recruitment rate, if we assume the upper boundary of the RED zone is 40% and the lower boundary of the GREEN zone is 60% (designating unacceptable and

- acceptable recruitment respectively), the sample size required for analysis given 80% power and one-sided 5% alpha would be at least N=42 (total screened participants).
- ii. Based on treatment fidelity (defined as having completed the ET assessment and having a written management plan or having been given written resources), if we assume the upper boundary of the RED zone is 60% and the lower boundary of the GREEN zone is 80%, the sample size required for analysis given 80% power and one-sided 5% alpha would be at least N=38 (intervention only).
- iii. Based on follow-up at 90 days, if we assume the upper boundary of the RED zone is 60% and the lower boundary of the GREEN zone is 80%, the sample size required for analysis given 80% power and one-sided 5% alpha would be at least N=38 (total randomised).

The sample sizes across criteria (i)-(iii) are at different levels; (i) is at the level of screened patients, whereas (ii)-(iii) are at the level of recruited patients. To meet criteria (i) we need ns \geq 42 (although we will screen approx. ns \geq 190 (i.e. (1/0.40) × nr (76)) where 0.40 is the expected proportion uptake of the total number screened), and for (ii)-(iii), we need nr = 76 (38 per arm) based on (ii)).

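### The fidelity criterion that sets N=76 in section 9.1 is not the one section 2.2 will apply, and the protocol does not clearly fix the latter's thresholds before randomisation

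*Protocol*

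**What the plan says.** **Sample size (Protocol, 9.1, criterion ii).** Fidelity is "defined as having completed the ET assessment and having a written management plan or having been given written resources". The calculation takes it that the "upper boundary of the RED zone is 60% and the lower boundary of the GREEN zone is 80" per cent, and concludes that the number needed "given 80% power and one-sided 5% alpha would be at least N=38 (intervention only"). The closing paragraph of 9.1 attributes the randomised total of 76, 38 per arm, to this criterion.

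**Progression criteria (Protocol, 2.2).** The fidelity entry in the traffic-light list has no percentages. Its ratings are to come from the bespoke fidelity tool, and "the progression criteria will be developed once the tool has been finalised". Under the WP1 outcomes, 2.2 gives that tool two jobs: checking delivery against the protocol and manual, and judging how well it was delivered. A researcher completes it when the three-month intervention ends. The Trial Summary and the table in 2.3 also tie fidelity to the tool.

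**Dates.** The table in 2.3 puts both the manual and the tool at "9 months after project commencement"; 2.2 repeats this for the manual ("A training and supervision manual (nine months after project commencement"). The Study Flow Chart lists development of both under WP1, months 1-6, and then shows "WP2: Feasibility RCT and Embedded Process Evaluation - Months 7-16".

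**The concern.** Section 9.1 presents its boundaries as the traffic-light zones against which feasibility will be tested. A reader of 9.1 would expect fidelity to be judged on a documentary yes/no definition at 60% and 80%. A reader of 2.2 would expect a tool that also scores quality, with boundaries still to come. The two sections do not refer to each other.

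Two things are at stake. First, fidelity is the only criterion that requires 76 randomised participants, so the justification of the sample size depends on which version applies. Second, a threshold chosen after delivery has started carries less weight than one fixed beforehand. Section 6.4 says that care providers cannot be blinded, so how delivery is going would be visible to those close to the trial.

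This is not a detail that can be left to a statistical analysis plan, because the protocol itself states both versions.

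**Working it through.** **1. What drives 76.** As stated in 9.1, recruitment needs 42 screened, retention needs 38 randomised in total, and fidelity needs 38 in the intervention arm. With 1:1 allocation (6.3), only fidelity leads to 2 × 38 = 76. Without it, the largest requirement at the randomised level would be 38.

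**2. Reproducing 38.** Inputs from 9.1(ii): p0 = 0.60, p1 = 0.80, one-sided alpha 0.05 (z = 1.645), power 0.80 (z = 0.842). The one-sample formula for a proportion is

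n = [(z₀.₉₅ √(p0(1−p0)) + z₀.₈₀ √(p1(1−p1))) / (p1−p0)]²

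= [(1.645 × 0.4899 + 0.842 × 0.4000) / 0.20]² = 32.63.

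With the continuity correction, where d = p1 − p0,

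n' = (n/4) [1 + √(1 + 2/(n d))]² = (32.63/4) [1 + √(1 + 2/6.526)]² = 37.46, rounded up to 38.

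The same steps for recruitment (0.40 v 0.60) give 41.95, rounded up to 42, also as stated. The method is therefore identified and the arithmetic is right. An exact one-sided test at n = 38 rejects RED at 29 or more successes, with alpha 0.027 and power 0.784, which is close to the stated 80%.

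**3. The two criteria side by side.**

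| | Section 9.1(ii) | Section 2.2 |
|---|---|---|
| Measure | Yes/no: assessment, with a written plan or written resources | Bespoke tool |
| Quality of delivery | Not covered | Covered |
| RED / GREEN | 60% / 80% | Not yet set |
| Role | Sets N=76 | Sets the progression rating |

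**4. How far N depends on the boundaries.** The protocol gives no tool-based boundaries. The pairs below are assumptions chosen only to show sensitivity, using the formula in step 2 at the same alpha and power.

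| RED / GREEN | Corrected n | Per arm | Total |
|---|---|---|---|
| 70 / 90 | 30.11 | 31 | 62 |
| 60 / 80 (section 9.1) | 37.46 | 38 | 76 |
| 50 / 70 | 41.34 | 42 | 84 |
| 70 / 85 | 55.87 | 56 | 112 |
| 65 / 80 | 62.36 | 63 | 126 |
| 60 / 75 | 67.37 | 68 | 136 |

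Holding the arm at 38, exact power is 0.92 for 70/90, 0.77 for 50/70, 0.66 for 70/85 and 0.51 for 60/75. If the tool yields a graded score rather than a proportion of participants, this formula does not apply until the score is dichotomised.

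**5. Timing.** The flow chart has the tool and manual developed in months 1-6; 2.3 has them due at month 9. WP2 begins in month 7. On the first date the thresholds can precede randomisation. On the second they may not: if recruitment opens at the start of month 7, the end of month 9 is three months into the six-month recruitment period. The tool is completed after three months of intervention, so its first scores would fall at about month 10 or later.

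**The case against.** **Timing.** The strongest reply concerns the dates. A reader might infer from 2.3 that the thresholds will certainly be set after participants have been randomised and treated, and that they could be fitted to the fidelity results. The documents do not support this. The flow chart places the work in months 1-6, so late thresholds are possible, not certain. Even at month 9, no completed tool scores should yet exist. What stands is that the protocol gives two dates, and that on the later one the boundaries could be chosen while delivery is being observed informally.

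**Consequence.** Section 2.2 says the outcomes are reviewed together and that an amber or red rating need not stop progression. Section 9.2 reports fidelity descriptively, and independent committees oversee the trial. No single fidelity test decides the outcome, so the conflict does not invalidate the trial. But 6.9 and 13.1 still make progression depend on minimum success criteria, and 9.1 justifies N by the power of this comparison.

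**Attrition.** A reader might also infer that power falls because people who leave before the three-month point cannot be scored. The protocol nowhere says so. The 9.1 definition rests on documents that can be checked after someone has left, and the tool is completed by a researcher. No loss of power is claimed on that ground.

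**Choice of remedy.** The Trial Summary, 2.2 and 2.3 all favour the tool; only 9.1 uses the yes/no definition. It would go too far to say that the tool must become purely descriptive.

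**Conclusion.** The point holds as an internal contradiction. Sections 9.1 and 2.2 give different fidelity criteria, and the one that produces N=76 is not the one that 2.2 will rate. The figure of 38 is correct for its own criterion; the stated 80% power and one-sided 5% alpha do not carry over to a measure whose boundaries have yet to be set.

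If the 9.1 criterion is adopted throughout, N is unchanged at 76. If tool-based boundaries differ, the supporting total could plausibly lie anywhere from 62 to 136. That range rests on the assumed pairs in the table and on the tool giving a proportion of participants.

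The conflict over dates is secondary but real. It leaves open whether the threshold for the size-setting criterion will be fixed before the first randomisation.

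**What to change.** State one fidelity criterion, with its RED and GREEN boundaries, in both 2.2 and 9.1, fixed before the first participant is randomised.

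- **Simplest route.** Put the 9.1(ii) definition in 2.2 with Green at 80% or more, Amber from 60% to below 80%, and Red below 60%. Use everyone randomised to the intervention as the denominator, and count anyone without documented delivery as not achieved. Keep the bespoke tool as a separate measure of quality. N stays at 76.
- **Alternative.** If the sponsor prefers a tool-based criterion, fix its thresholds before the first randomisation and restate the sample size justification in 9.1 to match. The required N may change.

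On either route, reconcile the due dates of the tool and manual in 2.2 and 2.3 with the months 1-6 plan in the flow chart, and align the Trial Summary.

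The first route costs only protocol wording and a corrected date. The second adds a fresh sample size calculation and the need to finish the tool before recruitment opens.

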2.3 Table of Endpoints and Outcomes

Objectives	Outcome Measures	Timepoints of Evaluation
WP1: Primary Objective: to develop	Training and supervision manual for ET workers	9 months after project commencement
communication, training, and trial	Fidelity of implementation tool	9 months after project commencement
materials	Audio, blog, event, film, and webpage content	18 months after project commencement
WP2: Primary Objective: to determine	Delivery of ET at each site	At end of nine-month feasibility trial period
the acceptability and feasibility of a full RCT	Number screened, eligible, and recruited	At end of feasibility trial period
	Outcome measure completion rates	Baseline, 42-days (±7 days), and 90- days (±7 days) post-baseline
	Intervention adherence and fidelity (based on bespoke fidelity tool)	At end of nine-month feasibility trial period
	Retention rates	90-days (±7 days) post-randomisation
	Proportion transferred or released during follow-up	At end of nine-month feasibility trial period
	Completeness of care plans, case notes, and	18 months after project commencement

	resource use questionnaires	
	Potential cost of ET BIA feasibility	18 months after project
		commencement 18 months after project
	assessment	commencement
	List of suitable variables	18 months after project
	for a social ROI	commencement
	Refined IPT, logic model,	18 months after project
	and delivery platform	commencement
WP2: Secondary Objective: to collect patient outcomes data to inform a full RCT, including assessing the acceptability of the measures used	CANFOR-R	Baseline, 42-days (±7 days), and 90-
		days (±7 days) post-baseline
	ASCOT SCT4	Baseline, 42-days (±7 days), and 90-
		days (±7 days) post-baseline
	EQ-5D-5L	Baseline, 42-days (±7 days), and 90-
		days (±7 days) post-baseline
	ICECAP-A	Baseline, 42-days (±7 days), and 90-
		days (±7 days) post-baseline
	ReQoL-10	Baseline, 42-days (±7 days), and 90-
		days (±7 days) post-baseline
	Resource usage	Baseline, 42-days (±7 days), and 90-
		days (±7 days) post-baseline

3. STUDY DESIGN

An exploratory framework will be used to gather preliminary information about the ET intervention and feasibility of conducting a full-scale trial. The study will include:

WP1: preliminary work, including development of communication, training, and trial materials.

WP2: a feasibility RCT and embedded formative process evaluation. The RCT will be a pragmatic, two-site, parallel arm, individually randomised RCT. Prison systems will be reviewed to identify people who meet the initial inclusion and exclusion criteria. These people will then be invited to take part in the study. Prisoners who consent will complete an ET screen (this timepoint will be defined as 'baseline'). Those scoring positively on the ET screen will be eligible for the feasibility RCT and will be consented to the study before being randomised to the intervention or social care as usual. Prisoners randomised to the intervention will undergo a full ET assessment, and those with higher-level social care needs will be allocated to ET, whilst those with lower-level social care needs will be signposted to appropriate resources. ET will be delivered for three months. Follow-up will be for a total of three months with outcomes assessed at baseline, 42-days post-baseline (±7 days), and 90-days post-baseline (±7 days). A sample of prisoners who participate in the RCT will be invited to participate in interviews as part of the embedded process evaluation, along with the ET workers and their supervisors, and healthcare, prison, and local authority staff. At the end of the study, findings will be reviewed against progression criteria.

4. STUDY SETTING

The study will be delivered at two male prisons in England, each of which houses adults serving prison sentences. All activities will involve participants from both sites.

5. PARTICIPANT ELIGIBILITY CRITERIA

WP1:

Development of training and supervision manual and audio, blog, and film content:

Inclusion Criteria (experts by experience):

- Aged 18 or over
- Capacity to consent to participate in the study
- Experience of being in prison with social care needs or of supporting a peer in prison with social care needs

Inclusion Criteria (professionals):

- Aged 18 years or over
- Healthcare, OT, prison, or local authority staff

WP2:

Feasibility RCT and formative process evaluation:

Preliminary Inclusion Criteria (prisoners):

- Aged 18 years or over
- Resident in one of the two study prisons
- Serving a sentence with at least seven months to earliest release date (with no upper limit)
- Capacity to consent or personal or independent consultee who can provide assent⁴

Preliminary Exclusion Criteria (prisoners):

- Insufficient knowledge of English to complete the assessment or outcome measures⁵
- Unsafe for researchers to interview alone

Additional Feasibility RCT Inclusion Criteria (prisoners):

• Scores positively on ET screen (needs in two or more domains)

Inclusion Criteria (ET workers and professionals):

• Aged 18 years or over

_

⁴ Prisoners with high social care needs include those with cognitive impairments who lack the capacity to consent to participating in research and as such as often under-represented in research. Excluding people who lack capacity, and who are likely to have the most complex needs and be the most vulnerable, would introduce significant bias. Their exclusion would mean that we are unable to understand the impact of the intervention on the target population or meaningfully generalise our results. As a result, we consider that it is important to avoid excluding such participants from the research.

⁵ This is due to challenges associated with getting translators into prison to administer the measures. There is a translator service available on some telephones in prisons; however, prior experience has shown that this is not reliable, and accessing it is exceptionally challenging. We will record the number of participants that are ineligible due to insufficient knowledge of English.

[figure not shown]
Empowered Together (Coordinated Social Care in Prison)/ET IRAS ID: 361615 Version 1: 01/08/2025

• ET worker or healthcare, prison, or local authority staff

6. STUDY PROCEDURES

Participant journeys through the study are mapped below and described in the following sections:

Empowered Together (Coordinated Social Care in Prison)/ET IRAS ID: 361615 Version 1: 01/08/2025

6.1 Recruitment

Participant Identification and Screening

WP1:

The workshops focused on developing the training and supervision manual for ET workers will be advertised through the Association for the Director of Adult Social Services (ADASS), the Health and Justice Research Network at UOM, and social media platforms. The workshops focused on developing the audio, blog, event, film, and webpage content will be promoted through the ADASS Care and Justice Network, the Health and Justice Research Network, the Prison Reform Network, Shaping Our Lives, and social media platforms. Individuals interested in attending the workshops will contact the research team, who will confirm their eligibility before inviting them to take part.

WP2:

For the feasibility RCT, identification of prisoners eligible for participation will occur in two stages. First, the research team will review prisoner lists with prison staff to identify those who meet the following preliminary exclusion and inclusion criteria (see section 5). This group will be weighted with those aged over 50 2:1 to reflect the likely distribution of social care needs in this population. These individuals will be provided with a PIS and Informed Consent Form (ICF) and asked to consent to an interview using the brief ET screening tool (see section 6.2). This tool is aligned with the Care Act and has been adapted from the community for prison settings.

Next, those who consent will complete the brief ET screening tool which asks prisoners whether they (a) consider themselves to have any mental or physical health conditions or impairments or be neurodiverse, and (b) experience difficulties in social care domains such as clothing, food, hygiene, toileting, safety, and family relationships. A series of probing questions relevant to these domains are also asked. The ET screening will be carried out by a researcher to avoid bias from the ET worker developing a relationship and understanding of the needs of participants who later enter the control arm. Those scoring positively on the tool will be eligible for the feasibility trial and will be approached to take part in a further consent process. All participants in the trial will receive an ET screen; this does not, therefore, form part of the intervention, but the acceptability and feasibility of this element will be included in the study.

For the formative process evaluation, first, purposive sampling will be used to identify prisoners from the control and intervention arms of the feasibility RCT who are diverse in terms of their ages, disability statuses, ethnicities, mental and physical health conditions, offence types, sentence lengths, and social care needs. From among these individuals, an estimated ten case studies will be selected (six from the intervention arm and four from the control arm). In the applied scientific realist approach, there is no optimum sample size or saturation point and, as such, the final and proposed numbers of case studies might differ depending on the information obtained. Staff and prisoners will be contacted directly by the research team and invited to take part in interviews as part of these case studies. Additional consent will be sought to make field observations. A further ten prisoners from this group will be invited to interview to discuss the feasibility of the trial design. Attempts will also be made to interview those who have withdrawn from the feasibility RCT, for example due to being released or transferred. To do this, the research team will gain consent from all participants to obtain their locations from Offender Management Services at the prison. The Empowered Together (Coordinated Social Care in Prison)/ET IRAS ID: 361615 Version 1: 01/08/2025

team will also procure the appropriate permissions from the governor of the new prison and the local research and development (R&D) department.

Second, a purposive sample of an estimated N=2 ET workers, N=2 ET supervisors, N=10 prison staff, N=10 healthcare staff, and N=4 local authority staff will also be identified. These will cover a wide range of employers, locations, and roles in the prisons. The final and proposed numbers of participants may differ, depending on the knowledgeableness of interviewees and information obtained. Once some staff members have been identified through purposive sampling, we will ask them to name other staff who are knowledgeable about the interview topics to ensure that the most relevant people are interviewed (snowball sampling). All potential participants will be contacted directly by the research team and invited to take part in an interview. The study will adopt a realist approach, which assumes that the same intervention will not work in the same way everywhere and for everyone, and focuses on what works, for whom, in what way, and how. A key part of the realist approach involves ensuring the most appropriate people are interviewed; as a result, should the team find that our chosen informants are not the best placed to provide information or that more information is required, we will increase the number of interviews.

No advertising materials will be used for WP2.

Participant Payment and Reimbursement

WP1:

Expert-by-experience participants will be paid £25 per hour in line with NIHR and INVOLVE rates (if they are not currently in prison or on probation, consistent with HMPPS rules). Professionals will not be compensated for their time. All compensation arrangements will be outlined in the PIS.

WP2:

We are not permitted under HMPPS rules to provide people in prison with financial compensation for their time, even if they have left prison but were recruited in prison. There will also be no travel or refreshment expenses for this group, as researchers will be visiting them onsite. Professional participants will not receive compensation for their time or for travel expenses. All compensation arrangements will be outlined in the PIS.

